- Significant cardiopulmonary disease other than asthma (Examples: Cystic Fibrosis, complex congenital heart disease)
- Non-English Speaking

Enrollment targets

• 15 participants

Identifying and Recruiting Participants

A member of the research team will contact eligible participants by telephone and provide a brief summary of the study after review of EMR.

If the potential participant expresses interest in participation, the initial research visit (including consent/assent discussion and documentation and completion of initial study measures) will be scheduled at the Milford or Wilmington outpatient pulmonology office.

Study Procedures

This technology-enhanced asthma pilot study will be completed over 24 weeks using a hybrid approach with remote and in-person research visits. Participants with persistent asthma ages 12-17 will be recruited from Nemours DE Healthcare System Pulmonology Division.

The initial (week 0) and final (week 24) visits will be completed as in-person visits in the Wilmington or Milford, DE, Nemours outpatient pulmonology office. At the initial visit, study measures will be completed, and

participants will be trained on the use of technology for future remote visits (mobile spirometry device connected to mobile application for reporting of results and the use of the telehealth platform). At the initial study visit, in office (gold standard) spirometry will be completed as well as mobile spirometry. Interval monthly visits at weeks 4, 8, 12, 16, and 20 will be completed using remote study procedures with completion of mobile spirometry and measures of asthma control and sleepiness. See Table 1 for study timeline. The final study visit at week 24 will include similar procedures as week 0, including in-office spirometry.

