The estimated time for the remote visit is estimated to be 20-30 minutes. The study-specific Satisfaction and Usability Questionnaire will be completed at each visit, which will take approximately 5 minutes to complete. The study-specific demographic and psychosocial assessment tool will be completed at the baseline visit, which will take approximately 5-10 minutes to complete. The asthma history questionnaire will be completed at the baseline and final visit, which will take 5 minutes to complete. The 5-time asthma control test (ACT[®])²³ will be completed at each study visit as well as the 10-item Epworth Sleepiness Scale for Children and Adolescents (ESS-CHAD).²⁴ Participants will receive a pre-paid gift card at the time of study consent, which will be loaded with \$25 after each in-person study visit and \$10 after each remote visit (\$100 total for completion of all visits).

All paper forms used in the study (e.g., questionnaires) will be kept in a locked file cabinet. Only members of the research team will have access to the human subjects' data and identifying information. All data will be identified only by Subject ID and the master list linking the subjects' identities to the code numbers, as well as consent forms with participant names, will be kept in a password protected excel sheet on the Nemours secure server. All electronic study data will be stored in a folder on the Nemours secure shared drive, separate from the document linking participants to subject IDs, and only study personnel will have access to this folder.

Table 1. Study Timeline

Outcome measure	*Baselin e	**Study visit 2	**Study visit 3	**Study visit 4	**Study visit 5	**Study visit 6	*Final	
Time (Weeks)	0	4	8	12	16	20	24	
Demographic and Psychosocial Assessment tool	x							
Asthma history questionnaire	Х						Х	
Standard Spirometry	Х						Х	
Mobile Spirometry	Х	Х	X	Х	X	Х	Х	
Asthma Control Test [®]	Х	Х	X	Х	Х	Х	Х	
Epworth Sleepiness Scale (ESS-CHAD)	Х	X	X	Х	X	Х	Х	
Satisfaction and Usability Questionnaire		x	x	x	x	x	x	
*Visit and Measures will be completed in-person								

**Remote study visit using telehealth platform and mobile spirometry device

Statistical Considerations

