The primary outcome of **feasibility** will be evaluated by calculating recruitment and retention rates at each study time point (e.g. percent of approached individuals who consent to participant, percent of enrolled participants who complete each study visit). The percent of patients who are successful at producing mobile spirometry results at each study visit will be calculated. The percentage of participants who require additional training sessions due to difficulty using the device will be calculated. To measure **acceptability**, the Satisfaction and Usability Survey will be reviewed at the item-level, and specifically, responses of "agree" or "strongly agree" will be used as benchmarks of acceptability and feasibility of each item. Responses to the open-ended questions will be analyzed for consistent themes across participants. Finally, to measure **accessibility**, the investigators will measure the length of time required to complete all visits and the frequency of any technical or connectivity issues. The investigators will meet regularly to review data management procedures and discuss any errors. Prior to beginning analyses, the investigators will examine the distribution of the data and identify any potential outliers. The investigators will consult closely with the REACH Center biostatistician in analyzing the data.

Descriptive and comparative statistics will be employed to characterize patient factors associated with successful study completion (completion of \geq 80% of study measures). Categorical variables will be summarized by frequencies and percentages, and continuous variables summarized by mean and standard deviation. Correlations will be utilized to determine whether any patient factors (e.g. age, grade in school, severity of asthma) are associated with successful completion of the pilot (completion of \geq 80% of study measures). For specific Aim 3, changes in asthma control and sleepiness will be examined longitudinally for each participant. Data distributions and change over time will be evaluated. Mean differences will be tested for statistical significance using ANOVA.

REFERENCES:

- 1. (CDC). Most Recent National Asthma Data: National Center for Environmental Health; 2020 [cited 2022 October 5]. Available: https://www.cdc.gov/asthma/most_recent_national_asthma_data.htm.

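### The 80%-of-measures rule can code a child who never attends week 24 as a successful completer, though only if nothing was missed before then

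*Combined protocol and SAP*

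**What the plan says.** The Overview of the Study sets an exploratory objective: to find which family, demographic and social characteristics go with completing the program. The Statistical Considerations section carries this out with descriptive and comparative statistics, and with correlations to see whether factors such as age, school grade and asthma severity "are associated with successful completion of the pilot". Two sentences of that paragraph define completion, both as at least "80% of study measures". Neither names a visit or measure that must be present, and neither says what is counted in the denominator.

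The same section reports retention separately, under the primary feasibility outcome, as the "percent of enrolled participants who complete each study visit".

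Study Procedures describes a 24-week pilot with in-person visits at weeks 0 and 24 at the Wilmington or Milford office. Between them, "Interval monthly visits at weeks 4, 8, 12, 16, and 20 will be completed using remote study procedures". On the last visit it says: "The final study visit at week 24 will include similar procedures as week 0, including in-office spirometry".

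**The concern.** A share-of-measures rule does not ask whether the child reached the end of the study. Six of the 32 scheduled administrations (6/32 = 18.75%) fall at week 0, before any remote monitoring has taken place. Children who cannot produce reliable spirometry or understand the measures at that visit are screen failures, so this credit says little about completing the program. Another six fall at week 24, few enough that all of them can be missed without dropping below 80%.

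Week 24 is the only visit after baseline that requires travel. The Scientific Rationale lists transportation among the reasons for disparities and gives reduced travel burden as a reason for the remote approach. Failure to return at week 24 is therefore plausibly related to the social factors under study, yet the rule can record it as success. Such a child supplies no follow-up standard spirometry, no final asthma history, and no week 24 asthma control or sleepiness score.

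The rule can also rank children oddly. One who attends week 24 in full but misses two remote visits has 32 − 8 = 24 administrations, 24/32 = 75%, and fails. One who leaves after a perfect week 20 passes.

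**Working it through.** The plan gives the percentage but neither the total nor the number needed, so there is no stated count to reproduce. The count below comes from Table 1.

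**Inputs**
- Demographic and psychosocial tool: 1. The "demographic and psychosocial assessment tool will be completed at the baseline visit".
- Asthma history: 2. "The asthma history questionnaire will be completed at the baseline and final visit".
- Standard spirometry: 2 (weeks 0 and 24). For week 0 the text says: "At the initial study visit, in office (gold standard) spirometry will be completed as well as mobile spirometry".
- Mobile spirometry, Asthma Control Test and ESS-CHAD: 7 each.
- Satisfaction and Usability Questionnaire: 6 (weeks 4 to 24).

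Total: 1 + 2 + 2 + 7 + 7 + 7 + 6 = 32. Needed for 80%: 0.80 × 32 = 25.6, so 26.

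**Cumulative count for a child who misses nothing up to the week shown**

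| Week | At visit | Cumulative | Share of 32 |
|---|---|---|---|
| 0 | 6 | 6 | 18.75% |
| 4 | 4 | 10 | 31.25% |
| 8 | 4 | 14 | 43.75% |
| 12 | 4 | 18 | 56.25% |
| 16 | 4 | 22 | 68.75% |
| 20 | 4 | 26 | 81.25% |
| 24 | 6 | 32 | 100% |

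Leaving after week 20 passes on exactly the required count. Leaving after week 16 fails. Leaving after week 20 with one earlier miss gives 25/32 = 78.1% and fails.

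**Sensitivity to the denominator**, for a child complete through week 20 with no week 24 data:
- Satisfaction form also counted at baseline, as the Study Procedures text (every visit) would have it: 27/33 = 81.8%, pass.
- Visits: 6/7 = 85.7%, pass.
- Without the demographic tool: 25/31 = 80.6%, pass.
- Without the satisfaction form: 21/26 = 80.8%, pass.
- Only the four repeated measures: 23/27 = 85.2%, pass. On this count alone of those listed by measure, one earlier miss still passes (22/27 = 81.5%).
- Post-baseline administrations only: 20/26 = 76.9%, fail.
- Instruments each at least 80% complete: asthma history and standard spirometry stand at 1/2, so 5/7 = 71.4%, fail.

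**How often a perfect record to week 20 might occur.** The documents give no completion rate. Assuming independent measures with a common rate p, and baseline complete, the chance of no miss in the 20 administrations from week 4 to week 20 is p^20: 12% at p = 0.90, 36% at 0.95, 67% at 0.98 and 82% at 0.99.

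**Weight of one child.** The enrollment target is 15, so one child is 1/15 = 6.7%. If k children would otherwise be non-completers (k assumed), recoding one removes 1/k of that group: a half at k = 2, a third at k = 3, a fifth at k = 5.

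**The case against.** The strongest reply is that the program under test is remote monitoring. A child who does the baseline visit and all five remote visits without a miss has arguably completed that intervention. Failing the child for one missed office visit mixes engagement with remote monitoring and access to travel. This stands as a real cost of adding a week 24 condition. It does not rescue the present label, because the plan speaks of completing a pilot that it describes as 24 weeks long.

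A reader might infer that the rule groups late dropouts in general with finishers. The documents do not support that. On the Table 1 count a single earlier miss turns the late leaver into a failure, and under the lower assumed completion rates most late leavers would have such a miss.

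A reader might also infer that the report would contradict itself, with one child both a retention loss and a success. It would not. Per-visit retention and the measure-completion flag are different metrics, and the plan has no rule that labels a child a retention failure. Loss at week 24 stays visible in the primary feasibility outcome. What remains of the concern is that only the 80% flag, not retention, is related to patient factors, so separate reporting does not repair that analysis.

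Finally, the denominator is undefined, and two of the readings tried exclude the child. That is correct, and is itself a reason to write the definition down.

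**Conclusion.** The point holds in a limited form. As written, and counted over the 32 administrations in Table 1, the definition codes a child with no missed measure through week 20 and no week 24 data as a successful completer, at 26/32 = 81.25%. This assumes that the denominator is the Table 1 schedule and that every session to week 20 counts as completed. The plan does not say whether a mobile spirometry session stopped without a reliable result counts.

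The consequence is confined to late leavers with a perfect earlier record and to one exploratory analysis. The number of such children cannot be known from the documents. One might go further and infer that the analysis could be left with no non-completers. That would need several such children and no other failures, for example 3 of 15 leaving after a perfect week 20 while all others pass. Nothing in the documents makes that likely. The definition should be tightened before analysis because the group is small and the change is cheap, but the primary feasibility results are not at risk.

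**What to change.** In both patient-factor sentences of Statistical Considerations, define successful completion as attending the week 24 visit and completing at least 80% of the administrations scheduled in Table 1 (26 of 32). Report the 80% figure on its own as measure adherence. The same edit should state whether an unsuccessful mobile spirometry session counts as completed, and should reconcile Table 1 with the Study Procedures text on the baseline satisfaction form. If that form is counted, the threshold is 27 of 33, since 0.80 × 33 = 26.4.

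A threshold of 80% of post-baseline administrations (0.80 × 26 = 20.8, so 21 of 26) would also exclude the late leaver, but it is stricter than needed. A child with a full baseline who attends week 24 and reaches 26/32 overall has only 20/26 after baseline and would fail.

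The cost is a short change to the text and no new data. Slightly fewer children will count as completers, and the flag will then partly reflect access to the in-person visit. Reporting adherence beside it lets a reader separate the two.

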Enhanced Community-Based Asthma Monitoring Through Novel Technology

Protocol version #1 01.11.23

Study Site Contact Information

Nemours Children's Hospital, Delaware Division of Pediatric Pulmonology [name]								
PI	[name]	[contact]	[contact]					
Co-I	[name]	[contact]	[contact]					

Overview of the Study

The primary objective of the proposed study is to pilot test implementation of a protocol for enhanced asthma monitoring using novel technology, including mobile spirometry and remote study visits, for rural and medically underserved children with persistent asthma in Delaware and to determine its feasibility, acceptability, and accessibility. Additionally, the proposed study aims to explore patient and family demographic characteristics and social factors associated with successful completion of the program and to explore the preliminary effect of the enhanced asthma monitoring program on asthma control and sleepiness as a measure of daytime functioning.

Scientific Rationale

Asthma is the most common chronic disease of childhood with significant morbidity, mortality, and economic burden in the United States and in Delaware. Asthma affects up to 6 million children in the United States (US) with estimated healthcare costs of \$81 billion annually.^{1,25} Despite the significant financial resources utilized for asthma and despite advances in preventative medications, asthma-related deaths continue to occur with over 3,000 deaths annually in the US.¹ DE, in particular, is a national asthma hotspot with a higher than average prevalence of childhood asthma(12%).² Over 25% of DE high school students report a lifetime diagnosis of asthma, with even higher rates for racial and ethnically minoritized children. Of those children with asthma in DE, 65% experienced an asthma-related visit to their doctor in the past year.^{2,26}

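### Aim 3 tests seven-visit ACT and ESS-CHAD scores by ANOVA; a mixed model on all available visits, with confidence intervals, would lose less data and inform more

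*Combined protocol and SAP*

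**What the plan says.** The Overview of the Study sets an aim to "explore the preliminary effect of the enhanced asthma monitoring program on asthma control and sleepiness". The enrolment target is 15 participants, with no comparison group. Under Study Procedures, the ACT "will be completed at each study visit as well as the 10-item Epworth Sleepiness Scale", and Table 1 confirms both scores at all seven visits. Weeks 0 and 24 are in person, and "Interval monthly visits at weeks 4, 8, 12, 16, and 20 will be completed using remote study procedures".

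The Aim 3 analysis is three statements at the end of Statistical Considerations. The first sets the general approach: "changes in asthma control and sleepiness will be examined longitudinally for each participant". The second adds, without naming any visits or contrast, that distributions and change across time are to be assessed. The third gives the test: "Mean differences will be tested for statistical significance using ANOVA".

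Only the last concerns a test. The section does not name the visits compared, the error term, a rule for missed visits, a correction for unequal correlation between visits, or a confidence interval.

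**The concern.** The first two statements point to a within-child analysis over time, so the ANOVA is most naturally a repeated-measures ANOVA across the seven visits. That method has three drawbacks here.

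- **Missed visits.** In its standard form a child with one missing score leaves the analysis. The plan treats missed visits as a real possibility, because the "percent of enrolled participants who complete each study visit" is itself a feasibility outcome. Among 15 children, few may have all seven scores.
- **Correlation structure.** The uncorrected F test assumes in effect that any two visits are equally correlated. Monthly scores may well be more alike when closer together, and the test then rejects too often.
- **What is reported.** The six-degree-of-freedom test asks whether any visit differs from any other. Aim 3 seeks a preliminary effect, for which a later trial needs an estimated change and its precision. No interval is promised.

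At stake is how much of a small dataset contributes to the only effectiveness information the pilot produces.

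**Working it through.** The documents give no power, effect size, SD, correlation or missed-visit rate for Aim 3, so there is no plan figure to reproduce. The inputs from the documents are n = 15, one group, and seven visits (six follow-ups). All other inputs are assumptions. Scores are in SD units with a nominal 5% level.

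**1. Complete cases.** If each follow-up visit is missed with probability m, independently, a child has all seven scores with probability (1 − m)^6.

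| m | (1 − m)^6 | Expected complete, of 15 | Expected with weeks 0 and 24 = 15(1 − m) |
|---|---|---|---|
| 5% | 0.735 | 11.0 | 14.25 |
| 10% | 0.531 | 8.0 | 13.5 |
| 20% | 0.262 | 3.9 | 12.0 |

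**2. Power of complete-case seven-visit ANOVA.** Assume constant correlation ρ = 0.6 and a mean change rising linearly to 0.5 SD at week 24. The step per visit is 0.5/6 = 1/12, so the deviations from the mean are −3, …, +3 times 1/12 and their squares sum to 28/144 = 0.194. The noncentrality for k children is k × 0.194/(1 − ρ). With k = 15 it is 15 × 0.194/0.4 = 7.29 on 6 and 84 df, and power is 45%. Averaging over a binomial k with success probability (1 − m)^6 gives 33%, 23% and 11% at m = 5%, 10% and 20%.

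**3. The same question on all available visits.** A within-child test of visit that keeps every observed score, simulated under the same assumptions, has power of about 44%, 41% and 36%, with type I error near 5%.

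| m | Complete-case ANOVA | All available visits |
|---|---|---|
| 5% | 33% | 44% |
| 10% | 23% | 41% |
| 20% | 11% | 36% |

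**4. Type I error when correlation decays.** With complete data, no true change and AR(1) correlation of 0.5, 0.7 and 0.8 between adjacent visits, uncorrected repeated-measures ANOVA rejects 6.9%, 8.3% and 8.8% of the time. With the Greenhouse-Geisser correction the rates are 3.5%, 4.0% and 4.2%.

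**5. What an interval would show.** For the paired week 0 to week 24 change with 15 children and ρ = 0.6, the 95% CI half-width is about t × √(2(1 − ρ))/√15 = 2.145 × 0.894/3.873 ≈ 0.49 SD. Simulated means at constant correlation 0.4 and 0.8 are 0.60 and 0.34 SD; under AR(1) of 0.5 to 0.8 they run from 0.76 to 0.66 SD. The pilot therefore estimates change only coarsely, which a significance statement alone would not show.

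**6. The single week 24 contrast.** Step 3 concerns the overall visit test. For the week 24 v week 0 contrast alone, a mixed model gains little power over the paired difference. In simulation (constant 0.6, 0.5 SD) the model had 45.5% v 48.3% for the paired test at 5% missed, and 45.8% v 46.6% at 10%. With AR(1) 0.7 it had 29.0% v 27.7% and 27.5% v 25.3%. Its null rejection ranged from 2.5% to 6.0%. Its benefit for that contrast is that children without a week 24 score still contribute.

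**The case against.** The plan does not say that the ANOVA would delete incomplete children or go uncorrected. Greenhouse-Geisser correction is routine and brings the error below 5%. The losses in step 1 assume independent misses and would be smaller if misses cluster in a few children. The documents also promise that "The investigators will consult closely with the REACH Center biostatistician in analyzing the data", and Aim 3 is exploratory in a 15-child pilot. All of this stands and keeps the point minor. But the consultation is placed at the analysis stage and fixes nothing in advance, and correcting the F test does not recover incomplete children or supply an interval.

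Three stronger readings are tempting, and the documents do not support them.

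- *The ANOVA treats the visits as independent groups.* The test sentence does not exclude this, but the two statements before it describe change over time within each participant.
- *A paired week 0 v week 24 test is generally more powerful than a seven-visit test.* With no missed visits and correlation 0.6, the order depends on the assumed course of change. A linear change gives 52% paired v 45% seven-visit at 0.5 SD, but 90% for both at 0.8 SD. A 0.5 SD change held over weeks 8 to 16 and waning to 0.25 SD by week 24 gives 17% paired v 49% seven-visit.
- *Only a p-value will be reported.* The plan tests mean differences and elsewhere summarises continuous variables by mean and standard deviation, so mean changes will probably appear. What is missing is a commitment to an interval.

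**Conclusion.** The concern holds as a minor one. Read naturally, the Aim 3 test is a repeated-measures ANOVA that in standard form would keep about 11.0, 8.0 or 3.9 of 15 children at 5%, 10% or 20% missed per follow-up visit. It would then have power of about 33%, 23% or 11%, where an all-available analysis has about 44%, 41% or 36%. These figures rest on independent misses, constant correlation 0.6 and a linear change of 0.5 SD; none comes from the documents. The 7% to 9% rejection rate applies only if the test is uncorrected and correlation decays as assumed. The plan's silence on contrast and missed visits would by itself be missing detail; the reason to act is that a better analysis is available at almost no cost. The primary feasibility outcome does not use this test.

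**What to change.** Replace the ANOVA sentence with:

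> For each score, a linear mixed model with visit as a categorical effect and within-child correlation, using all available visits and assuming missing at random, will estimate the mean change from week 0 to each visit, with week 24 as the main contrast, with 95% CIs and small-sample degrees of freedom. The paired week 0 to week 24 change with its 95% CI and the number of scores at each visit will also be reported. Results are uncontrolled within-child changes.

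The correlation structure should be able to decay with time between visits, given step 4. The paired change is a simple check on the model, and the counts per visit show how much rests on the missing-data assumption.

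The cost is two or three sentences and slightly more analysis work. It needs no new data, visits or participants, only standard software and the biostatistician already named. The main downside is reliance on missing at random, which 15 children cannot test; the paired estimate omits children without a week 24 score (an expected 0.75 of 15 at 5% missed, 3 of 15 at 20%).
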